**Figure 1 DCS vs. Placebo for Treatment of Depression**

The data above provided initial evidence that DCS may be useful as an NMDAR-targeted antidepressant, but the time of onset for DCS alone was suboptimal for treating acutely depressed individuals (Figure 1).

The data below provides evidence of efficacy from a study of NRX-101 versus Lurasidone in patients with severe bipolar depression (MADRS  $\geq 30$ ) and Acute Suicidal Ideation or behavior (C-SSRS 4 or 5), after an initial stabilization with a single infusion of ketamine.

**Figure 2 Randomization to NRX-101 vs. Lurasidone following stabilization with ketamine**

Source: Javitt et. al. 2018

## 6.4 Investigational Therapy

In accordance with FDA experience with lurasidone being used to successfully treat depression in bipolar disorder, participants will be randomized on Day 1 in a 1:1 ratio (NRX-101:lurasidone + placebo) and will receive maintenance treatment with matched twice-daily oral capsules. Participants will continue oral therapy through Day 42, according to treatment assignment.

It is anticipated that participants will also be receiving concurrent bipolar disorder-directed treatment with various predefined combinations of medications. This treatment regimen will be maintained upon entry into the study. However, any use of lurasidone, quetiapine, aripiprazole, risperidone, brexpiprazole, olanzapine, cariprazine, or lumateperone, will be discontinued at study entry. The treating psychiatrist should ensure that any medications to be discontinued can be done so safely. At entry, at the discretion of the investigators or the delegated treating physician subjects may continue their mood stabilizers which should not change over the course of the trial. In addition, participants receiving olanzapine/fluoxetine combination will continue to receive the fluoxetine component.

## 6.5 Dose Selection

Lurasidone is an FDA-approved medication for depressive episodes associated with Bipolar I Disorder (bipolar depression) as monotherapy and as adjunctive therapy with lithium or valproate at doses of 20 mg to 120 mg daily. The target dose of 66 mg/day is based on the mean daily dose of lurasidone observed during the fixed titration phase of the lurasidone registration trial for its indication in bipolar depression ([Loebel et al., 2014b](#)) and further validated in the STABIL-B trial ([Javitt, et. al. 2018](#)). Up-titration are permitted if needed to doses of 99 or 132 mg/day, and down-titration are permitted to 33 or 49.5 mg/day, which span the range of doses used in clinical studies of lurasidone ([Loebel et al., 2014a](#); [Loebel et al., 2014b](#)).

DCS is well tolerated as a second-line treatment for TB at therapeutic split daily oral doses in the range of 500 to 1000 mg/day. Based on prior clinical results and animal studies, it is anticipated that therapeutic effects of DCS will be associated with plasma doses in excess of 25 µg/mL, which in turn are generally associated with daily oral doses in excess of 10 mg/kg (i.e., 700 mg/day for a 70 kg) individual. A starting daily dose at 700 mg DCS and 33 mg lurasidone will be used, and then titrated over 2 days to the target dose of 950 mg DCS and 66 mg lurasidone. Down-titration of DCS to 825 or 700 mg/day are available in the case of side effects to permit reduced dosing within the anticipated therapeutic range (700 – 950 mg/day). The maximum dose of 950 mg/day is within FDA-approved dosing limits for DCS.

# 7. OBJECTIVES

## 7.1 Primary Efficacy Objective

The primary objective of the study is:

- To test the hypothesis that treatment with NRX-101 is superior to lurasidone (a standard of care medicine) in improving symptoms of depression as measured by the Montgomery Åsberg Depression Rating Scale (MADRS-10) total score in participants with severe bipolar depression and subacute suicidal ideation or behavior (SSIB).

## 7.2 Secondary Efficacy Objectives

- To test the hypothesis that treatment with NRX-101 is superior to standard of care (lurasidone) in reducing suicidal ideation (MADRS item 10).
- To test the hypothesis that treatment with NRX-101 is superior to lurasidone in the change from baseline to Day 14 in MADRS total score.
- To test the hypothesis that treatment with NRX-101 is superior to lurasidone in reducing the frequency of suicidal thoughts, suicidality and risk (SIBAT Module 7).
- To test the hypothesis that NRX-101 is superior to lurasidone in reducing suicidal ideation or behavior as measured by the Clinical Global Impression of Severity of Suicidality Scale (CGI-SS)
- To test the hypothesis that NRX-101 is superior to lurasidone in time to treatment failure as defined as: study discontinuation due to adverse events; psychiatric hospitalization; or requiring a change in antidepressant treatment.
- To test the hypothesis that treatment with NRX-101 is superior to treatment with lurasidone in the subgroup of participants recently (i.e. within two weeks of enrollment) treated with approved medications for bipolar depression (olanzapine/fluoxetine, quetiapine, cariprazine, lumateprazole, or lurasidone).
- To test the hypothesis that treatment with NRX-101 is superior to treatment with lurasidone in the subgroup of participants recently (i.e. within two weeks of enrollment) treated with approved medications for bipolar depression.
- To further test the hypothesis that treatment with NRX-101 is superior to treatment with lurasidone in the subgroup of participants recently (i.e. within two weeks of enrollment) treated with any 5-HT2A agonist for the primary efficacy endpoint.

## 7.3 Additional Efficacy Objective

- To display NRX-101 vs Lurasidone change from baseline for each MADRS-10 question as well as the three Borenstein factors at each post-baseline evaluation including exit.

## 7.4 Safety Objectives

- To test the hypothesis that treatment with NRX-101 is superior to lurasidone (a standard of care drug) in reducing suicidality in depressed bipolar participants with SSIB, as measured by the Columbia Suicide Severity Rating Scale (C-SSRS)
- To test the hypothesis that remission from suicidality, measured as Week 6 percent with C-SSRS  $\leq 3$  will be superior for NRX-101 relative to lurasidone

[figure not shown]
- To test the hypothesis that participants treated with NRX-101 are less likely to suffer from akathisia than those treated with lurasidone as measured by the Barnes Akathisia Rating Scale (BARS)
- To test the hypothesis that fewer participants treated with NRX-101 will be discontinued for lack of efficacy or exacerbation of suicidality than participants treated with lurasidone.

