9.1.2 Treatment and Follow-up Periods

Participants that continue to meet MADRS and C-SSRS eligibility will be randomized to receive the first dose of blinded treatment on Day 1. This visit will be followed by Treatment Period visits at Days 7, 14, 28, and 42. Following completion of the Treatment Period, participants will be

contacted via telephone for follow-up on Day 70. In order to allow scheduling flexibility, and (considering pandemic related limitations), visit windows will be allowed as noted in Table 1. Participants will be withdrawn from the study if their urine toxicology screenings at two consecutive study treatment visits are positive for cocaine, opiates, non-prescribed amphetamines, or non-prescribed barbiturates.

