16.4.3 Other Exploratory Efficacy Endpoints

The following other efficacy endpoints will be explored:

• Remission from suicidality: A Kaplan-Meier lifetable will be constructed for the remission duration from response onset where remission is defined as reaching CSSR-S ≤ 2 and remaining through the study. Remission rate is defined as percent remaining in remission.

Collectively, symptom improvement will be evaluated by assessing changes in the secondary outcome measures within and between treatment groups for each of the following at the times specified on the Schedule of Study Activities:

- Montgomery Asberg Depression Rating Scale (MADRS) (Montgomery, Åsberg 1979)
- Clinical Global Impression of Severity of Suicidality Scale (CGI-SS)

- Concise Health Risk Tracking Self Report (CHRT-SR) and Clinician Rating (CHRT-C) scales (Trivedi et al., 2011)
- Brief Psychiatric Rating Scale (BPRS) (Overall and Gorham, 1962).

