Endpoint(s):	
Primary Efficacy Endpoint:
 
 
• Change from baseline over 42 days in MADRS total score.
 
 
Secondary Efficacy Endpoints:
 
 
• Change from baseline over 42 days in CGI-SS.
 
• Time to treatment failure (TTF).
 
• Change from baseline in Suicidal Thoughts on the MADRS (MADRS item 10).
 
• Change from baseline to Day 14 in MADRS total score.
 
• Change from baseline for each MADRS-10 factor at each post-baseline evaluation including exit.
 
• Change from baseline for the three MADRS-10 factors defined by Borenstein at each post-baseline evaluation including exit.
 
• Change from baseline in each item of the Suicide Ideation and Behavior Assessment Tool (SIBAT) Module 7 (clinical global impressions of frequency of suicidal thinking, severity of suicidality, and imminent and long-term risks).
 
• Change from baseline to endpoint (Day 42/exit) in MADRS total score in the subgroup of participants who were recently (within 2-weeks of enrollment) on approved medications for bipolar depression as well as the 5-HT2A subset.
 
• Percent in remission from suicidality at Day 42/exit (exploratory endpoint).
 

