Study Design:	
A multicenter, randomized, stratified, double-blind, parallel-group, two-arm outpatient study of 74 participants comparing NRX-101 to lurasidone in a 1:1 ratio for the treatment of bipolar depression in participants with Subacute Suicidal Ideation or behavior and not requiring hospitalization, as reflected by a rating of 3 or 4 on the C-SSRS at screening. A priori sample size suggests > 90% power based on effect size of >1 seen in phase 2 STABIL-B trial. There is 80% power to detect a 0.66 effect size; a 0.462 effect size would reach two-sided p=0.05.
 
Two interim analyses are planned. The first interim analysis (IA) assessing safety will be conducted six weeks after the first 30-35 participants have been followed for 6 weeks and the second IA assessing futility (primary efficacy endpoint) will be performed after the first 45-50 participants have been followed for 6 weeks.
 
Each interim analysis has a different objective with neither interim analysis spending any Type 1 error. The study will be stopped at the first interim analysis if Serious Adverse Events are deemed statistically significantly more common in the NRX-101 group compared to the lurasidone group in a manner deemed by the DMC to pose a potential danger to human subjects. The study will be stopped at the second IA for futility if the conditional power (CP) is less than 10%. In the event that the study is not stopped for either safety or futility, then enrollment will continue until a total of 74 subjects are randomized. This preserves two-sided p=0.05 for the final analysis.

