Inclusion Criteria:	
A patient is eligible for inclusion in this study only if all of the following criteria apply:
 
 
1. 18 to 65 years of age, inclusive, at Screening.
 
2. Able to understand and provide written and dated informed consent prior to Screening.
 
3. Deemed likely to comply with the study protocol, including communication of adverse events (AEs) and other clinically important information, including adherence to the text messaging component of the trial.
 
4. Will follow medical directions for psychiatric care, as appropriate, per the standard of care.
 
5. Resides in a stable living situation. A stable living situation will be defined as a minimum of 3 months at the same address with a reasonable expectation that the situation will continue such that the patient's ability to participate in the study will not be affected. Please note that housing in a shelter of any kind will not be deemed stable housing.
 
6. Previously diagnosed and treated for Bipolar Disorder (BD) I or II according to the criteria defined in the DSM-V.
 
7. Has an identified reliable informant/care partner that is willing to provide information and/or supportive care as necessary.
 
8. The diagnosis of BD will have been made by a psychiatrist or other qualified licensed psychiatric provider able to render a diagnosis and be supported by the MINI 7.0.2.
 
9. Treatment with a medication indicated for use in bipolar disorder in the past five years (See Appendix 2 for list).
 
10. Confirmed active suicidal ideation, (without the intention to act) as evidenced by an answer of 'Yes' on item 3 and/or item 4 and not requiring hospitalization at Screening and an answer of "No" on item 5 of the C-SSRS within 4-weeks of Screening.
 
11. A total score greater than or equal to 30 on the 10 items of the MADRS.
 

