### 17.1.3 Additional Efficacy Endpoints

The following other efficacy endpoints will be explored:

- **Remission from suicidality:** A Kaplan-Meier lifetable will be constructed for the remission duration from response onset where remission is defined as reaching CSSR-S  $\leq 2$  and remaining through the study. Remission rate is defined as percent remaining in remission.

Collectively, symptom improvement will be evaluated by assessing changes in the secondary outcome measures within and between treatment groups for each of the following at the times specified on the Schedule of Study Activities:

- Montgomery Asberg Depression Rating Scale (MADRS) ([Montgomery, Åsberg 1979](#))
- Clinical Global Impression of Severity of Suicidality Scale (CGI-SS)
- Concise Health Risk Tracking – Self Report (CHRT-SR) and Clinician Rating (CHRT-C) scales ([Trivedi et al., 2011](#))
- Brief Psychiatric Rating Scale (BPRS) ([Overall and Gorham, 1962](#)).

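### The SAP defines remission from suicidality as C-SSRS ≤3 in its safety objectives but ≤2 in section 17.1.3; under ≤3 a patient who enters and stays at 3 counts as remitted

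*SAP*

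**What the plan says.** The SAP uses the label 'remission from suicidality' in three ways.

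- **Safety objectives (SAP synopsis and section 7.4).** NRX-101 is to be shown superior on "remission from suicidality, measured as Week 6 percent with C-SSRS" ≤3. This is a proportion at one time point. The protocol's safety objectives (synopsis and section 7.4) contain nothing equivalent.
- **SAP section 17.1.3.** "A Kaplan-Meier lifetable will be constructed for the remission duration from response onset where remission is defined as reaching" C-SSRS ≤2 and staying there to the end of the study; then "Remission rate is defined as percent remaining in remission". Protocol section 16.4.3 has the same rule: "where remission is defined as reaching CSSR-S ≤ 2 and remaining through the study".
- **Synopsis endpoint list (SAP and protocol).** "Percent in remission from suicidality at Day 42/exit (exploratory endpoint"), with no cut-off.

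On entry scores, the SAP design synopsis describes the population "as reflected by a rating of 3 or 4 on the C-SSRS at screening". Inclusion criterion 10 asks for a yes "on item 3 and/or item 4 and not requiring hospitalization at Screening", with a no on item 5. Protocol section 9.1.2 carries this forward to Day 1: "Participants that continue to meet MADRS and C-SSRS eligibility will be randomized".

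Protocol section 7.5 and SAP section 8 differ from criterion 10: they describe a yes to items 3 and 4 together.

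**The concern.** One label has two cut-offs, and nothing in either document explains why. SAP section 13 says that the SAP prevails over the protocol, but that cannot resolve a conflict inside the SAP. The synopsis endpoint does not settle it either. Its label and its exploratory status point to 17.1.3, while its form, a percentage at Day 42, is that of the safety objective.

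The looser cut-off is also a poor definition of remission for this population, because it includes a score at which patients are eligible to enroll. Remission from suicidality is a result readers of this trial will look for. As the SAP stands, a quoted rate could include patients no better than at entry, and a reader could not tell which cut-off had been used.

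**Working it through.** The point concerns a definition, so there is no plan figure to reproduce. The check is to apply each cut-off to the eligible entry scores and then ask what follows for rates and differences.

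**1. An unchanged patient.** Eligible entry scores are 3 and 4 (criterion 10, design synopsis).

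| Entry score, unchanged at Day 42 | ≤3 rule | ≤2 rule |
|---|---|---|
| 3 | remitted | not remitted |
| 4 | not remitted | not remitted |

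Let s be the share entering at 3. If nobody changes, the remission rate is s under ≤3 and 0% under ≤2. The documents do not give s. With 37 per arm (SAP section 18.2) and assumed values of s:

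- s = 0.25: 37 × 0.25 = 9.25, about 9 patients
- s = 0.50: 37 × 0.50 = 18.5, 18 or 19 patients
- s = 0.75: 37 × 0.75 = 27.75, about 28 patients

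Under ≤2 the count is 0 in each case.

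**2. Rate within an arm.** Anyone at ≤2 is also at ≤3, so the ≤3 rate is never below the ≤2 rate. It is higher by exactly the proportion who end at 3.

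**3. Difference between arms.** The following is illustration only; every rate is an assumption. Suppose 50% on NRX-101 and 30% on lurasidone are at ≤2 on Day 42, whatever their entry score. The ≤2 difference is 20 points.

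*(a) All other patients keep their entry score.* The ≤3 rate is r + (1 − r)s, where r is the ≤2 rate, and the difference is 0.20(1 − s). Power is for a two-sided Fisher exact test at 0.05, by full enumeration. The SAP plans no such test of this proportion; the test serves only as a yardstick.

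| Rule | NRX-101 | Lurasidone | Difference | Power |
|---|---|---|---|---|
| ≤2 | 50% | 30% | 20 points | 32% |
| ≤3, s = 0.25 | 62.5% | 47.5% | 15 points | 18% |
| ≤3, s = 0.50 | 75% | 65% | 10 points | 11% |
| ≤3, s = 0.75 | 87.5% | 82.5% | 5 points | 5% |

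*(b) Some lurasidone patients worsen.* Let a share y of lurasidone non-remitters who entered at 3 rise to 4 or above, and none on NRX-101. The difference becomes 0.20(1 − s) + 0.70·s·y. It returns to 0.20 when 0.70y = 0.20, that is y = 0.286, whatever the value of s above zero. At s = 0.50 and y = 0.40 the lurasidone rate is 0.30 + 0.70 × 0.50 × 0.60 = 51%, against 75% on NRX-101. That is 24 points with 48% power, more than under ≤2.

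So ≤3 can shrink or enlarge the difference, depending on who improves and who worsens.

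**4. What ≤3 measures.** SAP section 20.4 lists a C-SSRS score of 4 or more as an increase in suicidal ideation. On score alone, ≤3 is the complement of that category: it records that the patient is not at 4 or 5.

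**5. Link to an analysis.** SAP section 17.2 lists change in C-SSRS to Days 14 and 42. Section 20.4 gives a Fisher exact test of a score of 4 or more. Section 20.5 gives a McNemar test within arms and a Jonckheere-Terpstra test between arms. None names the Week 6 proportion at ≤3.

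**The case against.** **The two rules may be two measures.** One is a single-visit percentage, the other a sustained state shown by a lifetable, so they could be distinct summaries that happen to share a name. The difference in form is real, and the fix keeps both forms. It does not justify different cut-offs under one label, and it does not make an unchanged score of 3 a remission.

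**Nobody may enter at 3.** If the wording in protocol 7.5 and SAP section 8 were applied literally, every patient would have endorsed item 4 and the unchanged-at-3 case would not arise. That is a fair condition on the example. However, criterion 10 appears in both documents with and/or, and the design synopsis says 3 or 4, so entry at 3 is permitted as written. The passages must be reconciled. The conflict of cut-offs stands either way.

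**An analysis exists in substance.** The Fisher test on a score of 4 or more nearly covers the complement of ≤3, and a McNemar test needs some two-way split. This stands in part: the fair criticism is that the ≤3 objective is not explicitly tied to an analysis, not that no related analysis exists.

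**A stronger reading a reader might infer** is that ≤3 tilts the comparison towards NRX-101, or, conversely, that it must dilute a true difference. The documents support neither. They give no remission rates, no entry distribution and no pattern of worsening, and the illustration moves in both directions under different assumptions.

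**Conclusion.** The point holds. The SAP gives one label two cut-offs. The ≤3 version does not measure remission in a population that may enter at 3, and the SAP's precedence rule does not choose between them. Within an arm, ≤3 cannot lower the reported rate and raises it if any patient ends at 3. In the extreme case of no change, the excess equals the share who entered at 3, which is unknown. That rests on criterion 10 and the design synopsis governing entry. No direction can be claimed for the between-arm difference.

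The reach is limited to safety and exploratory reporting. The hierarchy in SAP section 18.3 runs from MADRS to CGI-SS to time to treatment failure, and includes no remission measure. A reader might infer that the primary conclusion or its type I error is at risk; it is not. This should be corrected, but it does not threaten the trial's main analysis.

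**What to change.** Before database lock:

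1. In the SAP synopsis safety objectives and SAP section 7.4, change ≤3 to ≤2, to match SAP 17.1.3 and protocol 16.4.3.
2. State ≤2 in the SAP synopsis endpoint for remission at Day 42/exit.
3. If the ≤3 proportion is wanted, keep it under another name, such as 'no C-SSRS rating of 4 or 5 at Week 6', and do not call it remission.
4. State that the Week 6 proportion and the sustained measure in 17.1.3 are separate summaries. The 17.1.3 lifetable need not be replaced.
5. In SAP sections 20.1 and 20.2, say which remission 'time to remission' refers to, since section 17.1.4 defines a different one (MADRS ≤10).
6. Reconcile the C-SSRS item wording in protocol 7.5 and SAP section 8 with criterion 10.

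The cost is wording only, with no new data. The reported remission rate will be lower than under ≤3 if any patient ends at 3.

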## 8. STUDY DESIGN

This is a group sequential, multicenter, randomized, double-blind, parallel-group, two-arm study comparing NRX-101 (n=37) to lurasidone (n=37) in a 1:1 ratio for the treatment of bipolar depression in participants with subacute levels of suicidal ideation, as reflected by the patient answering “yes” to item 3 and 4 on the C-SSRS within 4-weeks of screening, and do not require hospitalization.

Participants will be screened to ensure study eligibility prior to randomization on Day 1. Randomized participants will take either oral NRX-101 or lurasidone and placebo, in accordance with their treatment assignment, for 42 days. Participants will return to the investigational site on Day 70 for a follow-up visit (see Study Schema, Figure 3). During these visits, multiple psychometric scales will be completed, and participants will be assessed for safety, including the risk of increase in depression or suicidal ideation to the point where inpatient care or an alternative treatment is indicated.

**Figure 3** Study Schema

**Table 1** Schedule of Assessments

Visit Number	Screening		Treatment				Follow up 
	1	2	3	4	5	6	
Study Day	Day -10 to -1	Day 1  Baseline	Day 7	Day 14 	Day 28 	ET/Day 42 	Day 70
Informed Consent	X						
Eligibility Review	X	X					
Randomization		X					
Demographics	X						
Medical History	X						
Psychiatric History	X						
MINI	X						
MINI Severity/Disability		X				X	
Subject Eligibility	X	X					
Physical Exam 	X					X	
Vital Signs, Weight 	X	X		X	X	X	
ECG 	X	X				X	
Pregnancy Test (Urine dipstick)	X	X					
Drugs of Abuse Screen (Urine dipstick) 	X	X	X	X	X	X	
Fasting Chemistry, Hematology	X					X	
C-SSRS 	X	X	X	X	X	X	
MADRS	X	X	X	X	X	X	
CGI-SS	X	X	X	X	X	X	
CHRT-C, -SR	X		X	X	X	X	
BPRS psychosis subscale	X	X	X	X	X	X	
BARS 	X	X	X	X	X	X	
PRISE	X	X	X	X	X	X	
Adverse Events		X	X	X	X	X	X
Concomitant Medications	X	X	X	X	X	X	X
Adherence device training 		X					
Dispense investigational product and review adherence 			X	X	X		
Site monitoring of adherence 				X	X	X	

 Follow up visit will be a phone call; the study visit may occur within  $\pm$  7 days of the scheduled day (anchored to the Day 1 visit).

 Day 1 procedures need to meet eligibility criteria and will be performed prior to first dose.

 Study visits occurring after Day 7 may occur within  $\pm$  3 days of the scheduled day (anchored to the Day 1 visit). Study visits 3, 4, 5, 7 may be done virtually, preference is through videoconference.

 Full physical exam (including a neurological exam and height) at Screening and Visit 6 will be performed, and a brief exam (Blood Pressure, Respiration Rate, Heart Rate, and Temperature) will be performed at subsequent time points.

 After 5 min at rest, supine or sitting systolic and diastolic blood pressure and heart rate are recorded at each indicated visit. Weight is measured only at Screening and Visits 2,4,5, and 6.

 12-lead ECG.

 Subjects who have 2 consecutive positive urine screens should be withdrawn from study, in case of a subject not being able to visit a site due to COVID-19 restrictions or impediments arrangements should be made for an outpatient test, or the investigators should note this and make an assessment during the tele visit, annotation should be included in the EDC why the drug screen text could not be done. In the case where the subject has 2 consecutive negative urine screens, the subject can skip

the next urine screen. Investigators can bring the subject in for a urine screen at any time if suspected drug use. Note: Since Cannabis use is not exclusionary, a positive UDS will not require that patient be withdrawn from the study.

 “Baseline” version should be administered at screening and “Since Last Visit” version should be administered at all other time points.

 Adherence device training should be performed pre-dose on Day 1 or with the first dose. Additional training will be provided as necessary. The subject’s cellphone number will be input in a secure field of the EDC by the study site personnel, this field will only be accessible to designated study site personnel. The system will send a text message at designated hours to the subject as a reminder to take study the medication. The subject must respond affirmatively to enable compliance tracking. Absence of a response or a negative response will trigger a notification to the site.

 Medication adherence will be reviewed and returned pills recorded.

 Sites will monitor / review compliance for a target goal of 85 percent compliance of all doses taken. If more than 2 consecutive doses are missed they should contact the subject and counsel the subject on the need for compliance before the next scheduled dose.

 Rating akathisia using BARS needs to be a video call if completed remotely and will be documented.

